## PROTOCOL SYNOPSIS

Investigation: Tailored information about the coronavirus SARS CoV2, Covid-19, the coronavirus pandemic, the coronavirus infodemic and digital sources of reliable health information for patients with chronic kidney disease stage 4-5, using information videos followed by a teach-back method. The research questions is whether tailored information followed by the teach-back procedure improves health literacy and digital health literacy, reduce anxiety, maintain self-perceived health and lower the risk of Covid-19. We will utilize updated reliable health information at the LNT website lnt.no and the Norwegian Health Authority websites helsenorge.no, fhi.no and imdi.no. The teach-back method will be used in the intervention group only, which aims to ensure that key messages in information videos are presented in a way that the patient can understand, correct any misconceptions and show strategies to critically assess digital health information.

Target population: Patients with advanced kidney disease (CKD stage 4 or 5).

Centre(s): Akershus University Hospital, Lørenskog, Norway.

Study Period: Estimated date of first patient enrolled: 07.12.20, and date of last patient completed: 31.12.23.

Main Endpoints: 

- Digital literacy, measured by eHEALS.
- Health literacy, measured by HLQ.
- Degree of concern for Covid-19, measured by Fear of corona scale.
- Self-perceived health, measured by EQ-5D-5L.

Design: Randomized prospective open clinical trial.

Inclusion Criteria: Age  $\geq$  18 years.  
CKD stage 4 or 5, including renal transplant recipients (defined as CKD5T).  
Written informed consent.

Exclusion Criteria: Positive SARS CoV2 test prior to the baseline visit or at the baseline time-point.  
Cognitive impairment.  
Any reason why, in the opinion of the Investigator, the patient should not participate.

Sample Size: n = 192, where we aim for inclusion of  $\geq$  50 patients with other native tongue than English or a Scandinavian language (Norwegian, Swedish or Danish).

## LIST OF ABBREVIATIONS AND DEFINITIONS / EXPLANATIONS OF TERMS

Abbreviation	Explanation
CFS	Clinical Frailty Scale
CKD	Chronic kidney disease
Covid 19	Coronavirus 19 disease, which is caused by SARS CoV2
eHEALS	eHealth Literacy Scale, a subjective measure of digital health literacy
EQ-5D-5L	European Quality of Life Group (EuroQoL) 5 Dimension 5 Level scale of self-perceived health
HLQ	Health Literacy Questionnaire, a subjective measure of functional, interactive and critical literacy
LNT	The Norwegian Association for Kidney Patients and Transplant Recipients
Personvern	Institution Data Protection Officer (term not in regular use, thus replaced with "Personvern")
PI	Principal Investigator
REK	Regional Ethical Committee
SARS CoV2	Severe acute respiratory distress syndrome coronavirus 2

## 1 INTRODUCTION

During the end of March 2020, the first wave of Covid-19 caused by the novel coronavirus SARS CoV2 hit Norway, and in particular counties Oslo and Akershus (1). This resulted in several hospitalizations due to Covid-19 in patients with advanced kidney disease at Akershus University Hospital, including cases of long-term hospitalization in critical care units and deaths. Reduced kidney function as well as frequent comorbid conditions in CKD patients, put this group at increased risk of Covid-19 (2). Moreover, SARS CoV2 enter human cells via endocytosis after binding angiotensin converting enzyme receptor 2, which is highly expressed in the lungs and the kidneys, and may in part explain the high prevalence of acute kidney failure in Covid-19 and the high mortality rate among these patients (3). Naturally, many CKD patients reported concern for Covid-19 and felt uncertain how to best deal with this new situation. With a new wave of Covid-19 currently sweeping across our region (1) and recent reports of increased morbidity and mortality during Covid-19 for CKD patients and transplant recipients (4), these groups of patients frequently report concern about their near future.

### **The severe acute respiratory distress syndrome coronavirus 2 “infodemic”**

A coronavirus “infodemic” has accompanied the coronavirus pandemic (5), both internationally and nationally, supplying the public with abundant information on the SARS CoV2 and Covid-19 including what damage it can do, implications for the economy and how individuals and societies can fight it. Norwegian health authorities have used mainstream media and their own designated websites, to provide the public with updated reliable health information (1, 6, 7). However, this information is not equally accessible for all citizens (8). Moreover, some material published in mainstream media and several sources of information on the Internet present inaccurate or false information, speculations and myths put forward by unreliable sources (9). Several initiatives to reduce health misinformation and improve self-management are emerging (8). Improved digital literacy among health care providers and patients would likely empower them to cope better with the current situation and help fight prevalent misinformation. Most patients at increased risk of Covid-19 frequently encounter health care personnel. Thus, efforts by health personnel to provide these patients with accessible and reliable information on the coronavirus and the coronavirus pandemic could make them cope better with the current situation, especially if the information can be tailored to a specific target group, e.g. CKD patients (10). Knowing facts may help coping with stress and anxiety. Knowing how to critically assess health information may further reduce stress. Around the world, there are several ongoing epidemiological studies on associations between various factors related to health literacy and anxiety (11), including CKD patients. However, there is to our knowledge no clinical trial focusing on how to tailor Covid-19 information for CKD patients, how to improve digital health literacy in CKD, how digital health literacy affects mental health in CKD or whether improved digital health literacy lower the risk of Covid-19 (12). At present, Norwegian studies on experiences with and understanding of Covid-19 are scarce and limited to pregnancy and cancer management (13).

### **Health literacy in chronic kidney disease**

Health literacy implies knowledge, personal skills and confidence to take action to improve health (14). Low health literacy is associated with medication non-adherence, a higher burden of disease and a higher mortality rate (15). Data on health literacy in patients with CKD are sparse and focus mostly on functional literacy, the ability to read and comprehend words and numbers (16). Other aspects of health literacy, like interactive and critical literacy are less studied in CKD. Interplay between health care providers and receivers are mostly studied for choice of renal replacement therapy (16). Critical appraisal of information is shown to be low in CKD patients (17), which is of particular importance in the current situation with abundant digital health information.

Digital health literacy implies ability to use communication technology to find, evaluate, create and communicate health information. It requires cognitive and technical skills and is influenced by motivation for and access to digital information (12). Patients with low digital health literacy are more prone to miss important information. Patients with low digital and low critical literacy are more susceptible to misinterpret available information (18). The national health authority websites has made Covid-19 information available in several languages (1, 6, 7). However, this information is practically inaccessible for patients with low digital literacy (12), and patients who do not speak English or Norwegian, must maneuver five steps on fhi.no before they can reach information in a language that they master (1).

Previous reports indicate that low-intensity intervention with tailored education targeted at specific patient populations may reverse unhealthy habits by improving knowledge and risk perception and promoting a healthy life style (19). This trial will investigate whether tailored education improves digital health literacy in a Covid-19 high-risk population like advanced kidney disease and make them cope better with current situation.

## 2 STUDY HYPOTHESIS AND OBJECTIVES, EFFICACY AND SAFETY ASSESSMENTS

### 2.1 Hypotheses

Hypotheses, based on existing data: Limited intervention with tailored information about SARS CoV2, Covid-19, the coronavirus pandemic, the coronavirus infodemic and input to critical assess available digital sources of health information for patients with CKD stage 4-5, followed by a teach-back method, will improve digital health literacy, health literacy, reduce anxiety, maintain self-perceived health and lower the risk of Covid-19.

### 2.2 Objectives

Primary objective:

- Digital health literacy, measured by eHEALS.

Secondary objectives:

- Health literacy, including functional, interactive and critical literacy, measured by HLQ.
- Self-perceived health, measured by EQ-5D-5L.
- Degree of concern for Covid-19, measured by Fear of corona scale

Additional objectives:

- Proportion of patients feeling overwhelmed by the amount of coronavirus information.
- Proportion of patients finding it difficult to get information about the coronavirus in their native tongue.
- Composite end-point of positive SARS CoV2 test, hospitalization and death regardless of cause during the first two years after the intervention.

### 2.3 Efficacy and Safety Assessments

In accordance with the primary and secondary objectives, we will evaluate the effect of tailored information followed by a teach-back method (20) on top of standard care. There are no risks related to participation in the study, hence no safety assessments will be made and there will be no safety evaluation after completion of the trial. During the first two year following inclusion we will record hospitalizations due to Covid-19, hospitalizations regardless of cause, deaths regardless of cause and positive SARS CoV2 tests from medical records at Akershus University Hospital.

## 3 STUDY POPULATION

### 3.1 Target Population, Number of Patients, Recruitment and Screening

The target population is patients with advanced kidney disease defined as CKD stage 4 or 5, including renal transplant recipients (defined as CKD5T), who receive health care at Akershus University Hospital. The sample size is set at n = 192, where we aim for inclusion of  $\geq 50$  patients with other native tongue than a Scandinavian language (Norwegian, Swedish or Danish) or English. Patients will be recruited from the Dialysis Unit, wards and outpatient clinic at the Department of Renal Medicine, Akershus University Hospital.

### 3.2 Inclusion and Exclusion Criteria

Inclusion Criteria:	Age $\geq 18$ years. CKD stage 4 or 5, who receive health care at Akershus University Hospital. Written informed consent.
Exclusion Criteria:	Positive SARS CoV2 test prior to or at baseline. Cognitive impairment Any reason why, in the opinion of the PI, the patient should not participate.

## 4 STUDY DESIGN AND MANAGEMENT

Single center, prospective, randomized, open clinical trial investigating effects of tailored information about the coronavirus and the coronavirus pandemic for patients with advanced kidney disease, utilizing information at the LNT and Norwegian Health Authority websites, followed by a teach-back method, on top of standard care.

**Study period:** Estimated date of first patient enrolled: 07.12.2020. The anticipated recruitment period is 3-4 months. Estimated date of last patient completed: 31.12.2023, which also includes data management, statistical analyses, manuscript preparation and publication. The baseline and final visit CRFs will be dated.

[figure not shown]
**Study duration:** Approximately 15 weeks. The effect of the study intervention (tailored information at baseline followed by a teach-back method within the next 7 days) is measured at the 3(-4) month final visit.

#### 4.1.1 Flowchart

	Screening and Baseline visit	Within next 7 days	3 (-4) month Final visit	24 month follow-up
Screening for inclusion in trial	•			
Eligibility assessment and study enrollment	•			
Obtaining written informed consent	•			
Semi-structured interview	•		•	
eHEALS, a measure of digital health literacy	•		•	
HLQ, a measure of functional, interactive and critical literacy	•		•	
Fear of corona scale, anxiety / concern for Covid-19	•		•	
EQ-5D-5L, self-perceived health	•		•	
Question: Difficulty finding information in native tongue	•		•	
Question: Feeling overwhelmed by Covid-19 information	•		•	
Interviewer's assessment of Clinical Frailty Score	•		•	
Randomization	•			
Presentation of websites, including LNT information videos	•			
Study intervention (teach-back method)		•		
Medical record assessment	•			•
Charlson comorbidity index	•			

#### 4.1.2 Study Visits, Assessments, Data Recording and Investigator Delegation Procedure

Three study visits will be performed as presented in the flowchart. The Investigators will conduct a semi-structured interview and fill in an electronic CRF, which will be dated to ensure correct follow-up time, and to correct for events occurring during the study period that might influence participant responses. Data will be recorded directly into the electronic CRF at the baseline and final visits.

At the baseline visit a semi-structured interview will be performed, followed by a presentation of the LNT website (21). By early December 2020 this website will contain 20 short videos with information tailored for patients with CKD and organ transplant recipients on the topics SARS CoV2, Covid-19, the coronavirus pandemic, the coronavirus infodemic and strategies to critical assess of available digital sources of health information. These videos also contain a short presentation of updates reliable health information sources at the Norwegian Health Authority websites fhi.no, helsenorge.no and imdi.no (1, 6, 7), included where they can find information translated to various languages and where they can find links to other reliable digital health information sources at these websites. The videos are created by the study group and will be filmed and edited at Akershus University Hospital. They will be made originally in Norwegian and English, followed by translation and dubbing to several other languages, similar to previous patient information projects at Akershus University Hospital (22). All study participants will be presented to this source of health information at baseline and asked to study it closely.

For patients randomized to the *control group*, the Investigator will present them with the information videos available at the LNT website (21) and the Norwegian Health Authority websites (1, 6, 7), which would be regarded as within the frame of standard care, although this service is seldom provided at present.

For patients randomized to the *intervention group*, the Investigator will take on a more active part and make a new appointment with the patient (a new study visit) within 7 days following the baseline visit, either as a regular meeting, a digital meeting (e.g. zoom) or a telephone meeting. The patient will be asked to seek information available at the LNT website and watch the information videos found at this website, plus seek information available at the Norwegian Health Authority websites, before the new study visit. At the study visit the patient will be asked to give a short resume of take home messages from these websites that he/she find useful in everyday life. They will be asked if they have any questions regarding the information presented at these websites, followed by a teach-back procedure, which aims to ensure that key messages are presented in a way that the patient can understand, correct any misconceptions and show strategies to critically assess digital health information. The patient will be asked to present their strategy to find updated reliable health information available on the Internet. The teach-back method aim to reveal topics where there is a need to further modify and/or repeat information to make it possible to understand for the patient.

For patients who do not speak any Scandinavian language or English, an Investigator who speaks the same language as the patient or a professional translator will attend baseline and final visits, plus the additional new study visit for patients randomized to the intervention group, to ensure adequate communication. The PI is responsible for providing appropriate training relevant for all study Investigators and has developed an interview guide. The PI has made a “delegation of tasks” listing of involved co-workers and their role in the project, and is responsible for updating this list. The PI will ensure that any new information of relevance to the performance of this study is forwarded to the clinical steering committee and any staff involved in the study. This is of particular relevance to Investigators who will perform interviews at study visits in another language than English or any of the Scandinavian languages. It is the PI responsibility to provide these Investigators with validated translations of questionnaires included in the interview. The Investigators will themselves translate the remaining part of the interview as they go along, which for this study most often will be the case for the Fear of corona scale

questionnaire. Please note that even though main language spoken at home and native tongue is recorded, ethnicity will *not* be recorded. Native tongue will *not* be used in subgroup analyses since this would not harmonize with the study purpose and patient concealment could become violated. The study design should ensure provision of tailored information regardless of the patients' native tongue or preferred spoken language.

The PI or his designate will assess medical record for each patient at baseline and at two years follow-up. The following information will be recorded at the baseline visit: CKD stage, modality of renal replacement therapy where appropriate and chronic medical conditions to calculate the Charlson comorbidity index. The following information will be recorded at two years follow-up: Positive SARS CoV2 test, hospitalization due to Covid-19, hospitalization regardless of cause and death regardless of cause.

To ensure adequate responses, study interviews during a dialysis session should be performed during the first two hours of dialysis to avoid impact of cerebral ischemia towards the end of the session in some patients.

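### In an open trial with a self-rated primary endpoint, section 4.1.2 does not stop the person who gave a patient's teach-back from taking that patient's final interview; separately, the Fear of corona scale may be translated on the spot

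*Protocol*

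**What the plan says.** **Who collects the outcomes.** Protocol 4.1.2: "The Investigators will conduct a semi-structured interview and fill in an electronic CRF". Data go straight into the electronic CRF at the baseline and final visits. The flowchart (4.1.1) places eHEALS, HLQ, the Fear of corona scale and EQ-5D-5L at both visits. eHEALS is the primary endpoint (2.2), and the list of abbreviations calls it a subjective measure.

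**Who delivers the intervention.** For controls, "the Investigator will present them with the information videos available at the LNT website". For the intervention arm, "the Investigator will take on a more active part and make a new appointment with the patient". This extra visit falls within 7 days of baseline, may be held remotely, and contains the teach-back. The final visit follows at 3(-4) months (section 4).

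**Blinding and analysis.** Section 5.2 states that there is no blinding. It keeps the study group away from the randomization scheme but says nothing on outcome collection. Section 5.3 compares change from baseline between arms by t-test.

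**What might separate the roles.** Section 4.1.2 mentions training, an interview guide and a delegation "listing of involved co-workers and their role in the project". The contents of the guide and the list are not shown. For patients who speak neither English nor a Scandinavian language, "an Investigator who speaks the same language as the patient or a professional translator will attend baseline and final visits". That does not say whether it is the same individual each time.

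**Translation.** The rule concerns "Investigators who will perform interviews at study visits in another language than English or any of the Scandinavian languages". For them, "It is the PI responsibility to provide these Investigators with validated translations of questionnaires included in the interview". Then: "The Investigators will themselves translate the remaining part of the interview as they go along". The protocol adds that this will most often concern the Fear of corona scale, a secondary endpoint (2.2).

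**The concern.** **Interviewer.** At the teach-back the patient explains how they look for reliable health information, and misunderstandings are corrected. Section 1 describes digital health literacy in much the same terms, as being able to find and evaluate health information. Three months later the patient rates that ability in an interview. If the interviewer is the person who coached them, the answer may differ from the one given to someone else. Only intervention patients can be in this position, so any such shift enters the between-arm difference in change scores. Unless interviewer identity is recorded and varies, the analysis cannot tell it from an effect of the teach-back.

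**Translation.** A scale translated afresh at each interview can be worded differently at the two visits and from patient to patient. That adds noise to the change score of a secondary endpoint.

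**Working it through.** **Step 1: the passages side by side.** In 4.1.2 the Investigator role conducts the final interview in both arms and gives the teach-back in one. No sentence in 4.1.2, 5.2 or elsewhere keeps one individual from doing both for the same patient, and none requires it. The supported statement is that the protocol permits it. Controls also meet an Investigator who presents the material, so only the increment from the one additional contact can differ by arm.

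**Step 2: what a shift would do.** The protocol gives no bias figure to reproduce, so this is illustration only.
- Inputs from the protocol: 160 completers (5.1) and 1:1 allocation (5.2), so 80 per arm; 5% level and independent-groups t-test on change (5.3).
- Assumed: no true effect; a shift of *d* SD of the change score in a share *s* of intervention patients; SD unchanged.
- Formula: noncentrality = *d* × *s* × √(80/2), 158 degrees of freedom, two-sided critical value 1.975. Example: 0.1 × 1 × 6.325 = 0.632, rejection rate 9.6%.

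| Share affected | d = 0.05 | d = 0.1 | d = 0.2 |
|---|---|---|---|
| 100% | 6.1% | 9.6% | 24.2% |
| 50% | 5.3% | 6.1% | 9.6% |
| 25% | 5.1% | 5.3% | 6.1% |

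Here *d* is only the part of a shift that is due to who asks the questions. Self-report bias from patients knowing their arm is not included and would remain whoever interviews.

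**Step 3: noise from on-the-spot translation (Fear of corona scale).**
- Assumed: score variance 1 per visit; correlation between visits 0.6; share *q* of patients affected; added error variance *e* per visit; correlation *r* of that error between the visits.
- Variance of change without the error: 2(1 − 0.6) = 0.8. Added: 2*eq*(1 − *r*). Ratio = 1 + *eq*(1 − *r*)/0.4. Effective number per arm = 80/ratio.
- Upper case: *q* = 50/192 = 0.26, *e* = 0.25. Lower case: *q* = 0.10, *e* = 0.10.

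| Case | r = 0 | r = 0.5 | r = 0.8 |
|---|---|---|---|
| Upper: ratio (effective n) | 1.163 (68.8) | 1.081 (74.0) | 1.033 (77.5) |
| Lower: ratio (effective n) | 1.025 (78.0) | 1.0125 (79.0) | 1.005 (79.6) |

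The upper case takes all 50 patients in the native-tongue target (5.1) as needing an interview in another language. That target is a minimum defined by native tongue, and language help is provided only for those who do not speak English or a Scandinavian language, so the share actually affected is not given.

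**Step 4: would a completely new final interviewer be better?** If every patient had to change interviewer and interviewers accounted for a share *v* of score variance (assumed), the ratio is 1 + *v*/0.4. For *v* = 0.01, 0.02 and 0.05 this is 1.025, 1.05 and 1.125, so 80 per arm is worth 78, 76 and 71 compared with keeping one interviewer throughout. Both arms would pay this cost, and it is not needed to solve the problem in Step 1.

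**The case against.** The strongest reply on the first part is that it rests on silence. The protocol speaks of Investigators in the plural and refers to a delegation list, training and an interview guide. Who sees which patient could well be settled there. This stands: the roles may already be separate in practice, and then one sentence in 4.1.2 is all that is missing.

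Several features soften the risk. Patients are handed the interview questions at both visits and need not answer all of them (6.2). The teach-back may be a single telephone or digital contact, and the rating comes about three months later. The Investigator nevertheless still interviews and records, so the risk is reduced but not removed.

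It can also be said that patients know their arm, so self-report bias persists whatever is done. That is true, and it limits the gain. Nor would the interviewer's contribution be wholly beyond checking: if some patients have a different interviewer and identity is recorded, a partial check is possible.

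On translation, the protocol already requires validated translations, and improvising is the fallback. The problem is confined to other-language interviews, falls on both arms and mainly concerns a secondary endpoint.

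A reader might infer more: that the protocol assigns the coach to take the final interview, that the eHEALS result will be biased in favour of the intervention, or that questionnaires in general are improvised. The documents support none of these. They neither assign nor forbid the overlap of roles, they give no size or direction for any shift, and they provide for validated translations first.

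**Conclusion.** The concern holds as a cheap improvement to a rule that is left too open, not as a demonstrated bias.

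On the first part, the protocol permits one person to coach an intervention patient and later take that patient's self-ratings, including the primary endpoint. The false-positive rates of 5.1% to 24.2% depend entirely on assumed shifts of 0.05 to 0.2 SD and on an assumed share of patients; the true figure could be close to the nominal 5%. The case for acting is that prevention needs only a rostering rule, whereas a check after the event would be partial at best.

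The second part is separate and of lower priority. Under the assumptions shown, 80 per arm on the Fear of corona scale is worth between about 69 and 80, and the loss may be negligible. It does not directly affect eHEALS.

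A reader might also conclude that nobody with earlier contact should take the final interview. That goes beyond the problem: both arms have a baseline interview, and excluding that interviewer brings the precision loss of Step 4.

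**What to change.** **Interviewer (4.1.2).** State that whoever gives a patient's teach-back does not take that patient's final interview, and that final interviewers are assigned by the same rule in both arms. For example, another Investigator on the delegation list gives the teach-back, and the baseline interviewer may take the final visit in both arms. Do not bar the baseline interviewer as such. Record interviewer identity in the electronic CRF and flag unavoidable exceptions, such as rare languages. If the delegation list already separates the roles, say so in 4.1.2.

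Cost: rostering among listed Investigators and one CRF field. The number of Investigators per language is not stated, so some exceptions are likely. Self-report bias from patients knowing their arm remains.

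**Translation (4.1.2), lower priority.** For the Fear of corona scale, replace on-the-spot translation with one fixed written translation per language, prepared before first use and read identically at both visits and in both arms.

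Cost: one short translation per language.

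### The stated question is tailored information plus teach-back added to standard care, but both arms get the information, so the comparison isolates only the extra follow-up visit

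*Protocol*

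**What the plan says.** **The question as stated.**
- The Synopsis: "The research questions is whether tailored information followed by the teach-back procedure improves health literacy and digital health literacy". No comparator is named in that sentence, although the same paragraph adds: "The teach-back method will be used in the intervention group only".
- The aim sentence in section 1 (Health literacy in chronic kidney disease) does not mention teach-back: "This trial will investigate whether tailored education improves digital health literacy in a Covid-19 high-risk population".
- Section 2.1 expects improvement from "tailored information about SARS CoV2, Covid-19, the coronavirus pandemic, the coronavirus infodemic and input to critical assess available digital sources of health information", followed by teach-back. No comparator is named.
- Section 2.3: "we will evaluate the effect of tailored information followed by a teach-back method (20) on top of standard care".
- The design statement in section 4 describes the trial as "utilizing information at the LNT and Norwegian Health Authority websites, followed by a teach-back method, on top of standard care".
- The study duration paragraph in section 4 defines the term: "The effect of the study intervention (tailored information at baseline followed by a teach-back method within the next 7 days".

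**The arms as delivered.**
- The flowchart (section 4.1.1) attaches the label study intervention to teach-back only. Presentation of the websites and videos is a separate baseline row.
- Section 4.1.2, on the videos and websites: "All study participants will be presented to this source of health information at baseline and asked to study it closely". It counts the presentation to controls as standard care, yet concedes that it is rarely offered today.
- For the intervention arm, section 4.1.2 adds an appointment within 7 days. Patients are asked to go through the material beforehand. At the visit they summarize what they found useful, may ask questions, and go through teach-back.

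**The analysis.** Section 5.3 compares change from baseline to the final visit between the arms with an independent-groups t-test.

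**The concern.** The aim, the efficacy statement and the design statement are the sentences from which a report's conclusion is usually built. Here they credit tailored information, or information plus teach-back, with the effect to be measured. Controls receive that information too.

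A positive result worded like section 2.3 would attribute to the package, relative to standard care, an effect observed only for the extra visit. A null result worded the same way would read as a failure of tailored information, on which the comparison is silent. The second case matters most to a hospital deciding whether to offer the videos at all, since by the Protocol's own account such a presentation is seldom part of present care.

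**Working it through.** **1. Does any stated figure depend on the definition?** Section 5.1 uses N ≥ 8/f² + (m − 1) with f² = 0.05. With m = 1 (m is not stated), 8/0.05 + 0 = 160 completers, and 160 × 1.2 = 192. Neither step refers to the content of the arms, so the figures are the same under either definition.

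**2. Are the shared videos the tailored information of the hypothesis?** Section 2.1 lists five subjects: the virus, the disease, the pandemic, the infodemic and critical appraisal of digital health sources. Section 4.1.2 lists the same five for the 20 videos. All 5 of 5 go to both arms.

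**3. What differs between the arms?**

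| Element | Intervention | Control |
|---|---|---|
| Baseline presentation of videos and websites | yes | yes |
| Request at baseline to study the material | yes | yes |
| Further request to review it before an appointment | yes | no |
| Visit within 7 days: recap, questions, teach-back | yes | no |

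**4. What does the t-test estimate?** Let C be the mean change under care as currently practised, V the effect of the baseline presentation (taken as equal in both arms), and T the added effect of everything in the last two rows, including any extra use of the material that the visit prompts.

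- Intervention: C + V + T
- Control: C + V
- Difference: (C + V + T) − (C + V) = T

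The package against care as currently practised would be V + T, and the information alone would be V. No arm shows C by itself, so neither quantity can be recovered from the comparison.

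**5. Illustration.** The documents give no effect sizes, so these values are assumed, in SD units.

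| T | V | Between-arm difference (T) | Package vs current care (V + T) |
|---|---|---|---|
| 0.2 | 0 | 0.2 | 0.2 |
| 0.2 | 0.3 | 0.2 | 0.5 |
| 0.2 | 0.6 | 0.2 | 0.8 |
| 0 | 0.6 | 0 | 0.6 |

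The first three rows give the trial the same result. The last gives a null result although the package works.

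**6. Can the two standard-care statements both stand?** If presenting the videos is standard care, the information cannot also be part of what sections 2.3 and 4 add to standard care. If it is not standard care, controls receive more than standard care. Either way, one set of statements has to change.

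**The case against.** The best defence is that one reading fits every section. Intervention patients get information and then teach-back, and controls get the information only. Section 4 describes what an intervention patient experiences in sequence, while the flowchart puts the label on the arm-specific step. On this view the terminology is loose but there is only one design, and it is disclosed in the Synopsis and in section 4.1.2.

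Much of this stands:
- A reader might infer two incompatible designs, or a risk that staff deliver the wrong arm. The documents do not support that, because section 4.1.2 is explicit about who gets what.
- A reader might infer that section 2.1 claims an effect of information alone. It does not. It makes a claim about the package, and only the aim sentence in section 1 leaves teach-back out.
- The split into shared information and randomized teach-back is not perfectly clean. The pre-visit request may raise use of the material in the intervention arm. That is why T above covers the whole visit with its preparation.
- The algebra is an identity and the SD values are assumptions. They show what cancels and are not evidence of how much.

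What does not stand is that disclosure settles the matter. Describing the control arm correctly in the procedures does not correct the aim, efficacy and design statements. Even as a package claim, the hypothesis is not tested against care without the information. Calling the videos standard care conflicts with the Protocol's own remark that the service is rarely provided, and with the fact that the study group makes the videos for this purpose.

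**Conclusion.** The point holds as a mismatch between the stated question and the randomized contrast. The comparison estimates the added effect of the follow-up visit within 7 days, with its preparation, given that both arms have been shown the tailored material. It does not estimate the effect of tailored information, or of information plus teach-back, over care as currently practised. Separately, the term study intervention means the package in section 4 and teach-back alone in section 4.1.1.

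In size, one of the two named components, covering all five subjects in the hypothesis, is shared by both arms. The conclusion rests on both arms receiving the baseline presentation as written and on that presentation acting alike in both.

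A reader might go further and infer that the trial is underpowered because teach-back is only part of the package. The documents do not support this. Section 5.1 does not tie f² to any contrast and says that no earlier trial data were available. No numerical error follows from this point. It should be corrected because it governs what the trial may conclude, while the conduct and the analysis can stay as they are.

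**What to change.** Change the wording only:

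1. Restate the research question (Synopsis), the aim sentence (section 1), the hypothesis (2.1), section 2.3 and the design and duration statements (section 4) along these lines: *the effect of an additional follow-up visit within 7 days (pre-visit request to review the material, recap, questions and teach-back), added to tailored videos and websites presented to both arms, versus that presentation alone*.
2. Use one definition of study intervention in sections 4 and 4.1.1.
3. Reconcile the standard-care wording in sections 2.3 and 4 with that in 4.1.2. Describe the control as information only, and say that this is more than care as currently practised.

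Patients, visits, staff, sample size and analyses are unaffected. The price is a narrower claim: the trial speaks for the added visit, not for tailored information as such.
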